#### **2.4.3 Kangaroo Care Studies and Weight Gain**

A prospective case-control study conducted by Biswas, Malpani & Ekka (2016) on newborns weighing less than 1.5kg in a tertiary level NICU at a teaching hospital in Central India,

found that the KC technique produced a daily weight gain of on average (23.99 vs. 15.58g,  $p<0.01$ ). A prospective study conducted on Kangaroo care (KC) showed it reduced neonatal deaths and neonatal sepsis, and enhanced growth outcomes in preterm infants. The study contrasted the efficacy of infant care using KC in the ward with the efficacy of infant care in Intermediate Intensive Care (IIC) in stable preterm infants (birth weight  $< 1100$  g) to stimulate the growth velocity up to term age adjustment. When they reached a weight of 1150 g, one hundred and forty-one infants were randomized to KC in the ward (n=71) or IIC (n=70). Infants in the KC group were transferred directly after randomization to the Kangaroo ward care (KWC) and those in the IIC category were cared for in the IIC until they reached a weight of 1250 g when they were relocated to the KWC. In both groups the average weight gains as well as weight, length, and head circumference were comparable at term corrected age. In the KWC group, there was a significant decline in IIC post-randomization stay and a rise in weight gain prior to discharge. The frequency of apnea within the IIC group was significantly increased. Early KWC is just as effective as IIC in enhancing the growth outcomes of stable preterm infants (birth weight  $< 1100$  g) at term gestation. Sharma, Murki & Pratap (2016) reported that KC had a positive and healthy effect on maternal care with stable premature infants weighing 1150g without adverse effects. Suman et al. (2008), however, found a significantly higher weight gain in the KC group compared to other studies, while Ramanathan et al. (2001) also reported a greater weight gain in the KC group during the first week of life than those in the control group (15,9±4,5 vs. 10,6±4,5 g / day).

Ghavane, Murki, Subramanian, Gaddam, Kandraju, & Thumalla, (2012) conducted an RCT study at one of the Hyderabad hospitals. The study compared the effect of KC and conventional care in a neonatal unit on growth and breastfeeding among VLBW infants at a corrected age of 40 weeks. One hundred and forty birth-weight neonates  $< 1500$  g were randomized. The study found that the average weight gain (g / kg / day) from time of

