***b) Section B: Infant's Kangaroo Care Progress Record (KCPR) or Data Sheet***

Section B assessed the progress of the premature infant in terms of primary and secondary outcomes. The primary outcome variables were weight gain and LOS, while the secondary outcomes were breastfeeding rate or feeding status. All nine (9) items were adapted from the original article by Singh, Amritanshu and Mukherjee, (2014) and Biswas, Malpani & Ekka, (2016) with a slight modification and format to satisfy the research goals relevant to the main and secondary monitoring requirements of the use of KC to assess outcomes. The variables consisted of baseline temperature, age of KC initiation (week/days), weight at KC initiation (g/days), weight gain velocity (g/days), duration of KC (in hour/day), duration of stay (days), types of milk (EBM or breastfeeding), initiation of breastfeeding (weeks) and weaning from breastfeeding (weeks) for both groups. The KCPR booklet was designed and presented to the

respective control and experimental groups. The difference in the KCPR booklet was the knowledge needed for the experimental group to get the input given to the control group for preterm infants (routine activities and standard care) and KC performance. The data for the preterm infants in the control group were documented according to standard practice care or routine practice in the NICU. [Please refer to Appendix F(a) and F(b)].

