### **3.16.4 Method of Data Collection for Infants**

The researcher recruited the control group of premature infants first and then the experimental group after the nursing intervention program had been completed. The preterm infants in both groups were recruited based on infant admission days and according to mother-infant dyad condition. Firstly, all preterm infants between 28 and 36 + 6 days of gestation (n=48) were recruited by the researchers to participate in the study. The first

recruitment was assigned to the control group. The second recruitment of preterm infants who conformed to the inclusion criteria, i.e. clinically stable and ready to perform KC, was assigned to the experimental group (n=48) after written consent was given by their mothers. Those whose mothers refused to participate were excluded from the study. In the experimental group, data from the preterm infants were collected from the recruitment day until they reached 3 months old. A total of 48 newborn preterm infants from the same setting were given routine care (under servo-controlled radiant warmer or in a cradle with room heaters or blankets) and matched by corrected age. Feeding mode at admission to either group was monitored and jotted down, according to the route of feeding: tube feed, spoon-feed or breastfeeding. Before allocation to a group, it was ensured that the preterm infant was tolerating enteral feeds (over 24 hours) and had no regurgitation at age 28 to 36+6 day weeks of gestation. Corrected age was calculated using the Premature Baby Corrected Age Formula and classified between 28 to 36+6 days weeks of gestation. The baseline weight was calculated from the birth weight and weight on recruitment at T0, and outcome weight gain calculated from the weight on discharge, T1, and T2; this was recorded in the KCPR booklet provided. The body weight of the preterm infant was documented, after removing its clothes, using an electronic weighing scale with an accuracy of 5g at least 2 hours after the last feed and twice a week on Tuesdays and Saturdays according to the hospital protocol for weighing babies. Body weight was measured using a T- scale machine and recorded in grams (g).

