After the preterm infants were allocated to the control group or experimental group, they were observed daily, and all observations related to the outcomes of the study were documented in the KCPR booklet i.e. velocity of weight, temperature before, during and after, mode of feeding, type of milk taken and duration of KC provided (in hours/day/week), date of admission and date of discharge in days. In the study by Biswas, Malpani & Ekka, (2016) temperature measurement was taken 10 minutes after KC. However, in this study the

temperature measurement was taken 10 minutes before, 20 to 30 minutes during KC and 10 minutes after the implementation of KC and a regular clinical examination was given in a minimal period of time to avoid hypothermia and cold stress. In the experimental group, duration of KC (in an hour/day) was measured from an accumulated daily 1 hour per day, 4 to 5 hours a week. However, according to Ludington-Hoe, Susan, Morgan, K. & Abouelfetoh (2008), KC is best provided 1 hour a day and 7 days a week until discharge. KC was continued until the premature infant was 3 months old, according to the study requirements. If any problems were detected during KC, they were either rectified or the preterm infant was disqualified from the study. Premature infants were discharged when they showed a good sucking reflex with breast or bottle feeding and had been gaining weight of more than 15g/day to 20g/day for at least three successive days and had achieved a predetermined weight of 1.7kg, in accordance with hospital protocol. On discharge, the nurses routinely advised mothers to come for follow-up until their infant had reached a weight of 2500 grams and to continue breastfeeding. For primary and secondary outcomes, the data from both groups were collected at T0, T1, and T2. The premature infants were followed-up until they were discharged. Conversations and communication between mothers and researchers continued through telephone calls or Whatsapp chat groups accordingly. All related information on KC was shared through the WhatsApp chat group among mothers in the experimental group so that they would remain KC compliant and continue KC at home.

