#### a) Infant Outcome Variables Data

In Phase I and Phase III, the outcome data were collected from the control group and experimental group of infants. The outcome data were recorded continuously from the day of recruitment at the corrected age of between 28 to 36/6 weeks of gestation in the NICU until the infants reached 3 months old after discharge. At any stage, if a premature infant in the experimental group did not meet the requirements for research (e.g. deteriorated during KC

or needed phototherapy treatment for jaundice), the infant was excluded from the study. During the two phases, similar outcome variables and confounding variables were obtained. The outcome variables reflected the outcomes of the premature infants. Specifically:

i) KC implementation duration in hours (in hours; 24 hours = 1 day); The duration of KC in the intensive care unit measures the number of hours the infant was attached to or bonded with their mother. According to the posttest it was measured in hours and days per week. According to the World Health Organization (2003), each KC session should ideally last at least 1 hour, in order to get the physiological effects and for brain development and maturation. In this study, the researcher decided to practice accumulative 1 hour per day and accumulative 4 to 5 hours per week (KC duration).

ii) Weight gain of the infant in daily weight (in a day; 1 day = 24 hours)

The weight gain of the premature infant represents the amount the infant's weight increased or decreased in a day. 1 day equal to 24 hours.

iii) The decrease in hospitalization stay or Length of hospitalization stay (LOS) in the NICU (in a day; 1 day = 24 hours);

The length of stay at the NICU measures the number of days the preterm infant was admitted to the intensive care unit and was treated in a day, 1 day equivalent to 24 hours. iv) Confounding variables

All standard demographic and clinical measures assessed by preterm infants with critical care were collected, including:

- demographic data: gestation, age, gender, ethnicity and weight gain for infants;
- type of milk (breastfeeding or formula milk)
- duration of feeding status i.e. week started and week discontinued breastfeeding and mode of feeding, bottle, or spoon-feeding.

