1.	Are there any statistically significant differences in mothers' perception, knowledge, perceived barriers regarding KC, and stress related to 'premature infants admission to NICU' after participation in the KC-EP?	Perception, knowledge, perceived barriers and stress related to premature infants' admission to NICU mean scores Effect of KC-EP KC performance (Ordinal data)	Descriptive - mean, SD, skewness and kurtosis Chi-square test, GLM, repeated measure (RM) & Pearson Eta Squared.
2.	Does kangaroo care improve weight gain patterns in premature infants between control and experimental groups at $T_0$ , $T_1$ , and $T_2$ ?	Weight gain patterns (grams) mean score KC compliance Duration (hours/weeks) Frequency and Percentage (Continuous data)	Descriptive – mean, SD, skewness and kurtosis Chi-square test, GLM and t-test.
3.	Does kangaroo care decrease the length of hospitalization stay for premature infants between control and experimental groups?	Length of hospitalization stay Frequency and percentage (Continuous data)	Descriptive – mean, SD, skewness and kurtosis Chi-square test, GLM and test
4.	Does kangaroo care improve breastfeeding rates for premature infants between control and experimental groups?	Breastfeeding rates KC compliance Frequency and percentage (Continuous data)	Descriptive – mean, SD, skewness and kurtosis Chi-square test, GLM and t-test.
5.	Are there any statistically significant differences in nurses' perception, knowledge, and practice regarding KC before and after participation in the KC-EP?	Perception, knowledge, practice mean scores Effect of KC-EP (Ordinal data)	Descriptive - mean, SD, skewness and kurtosis Independent t-test GLM, RM & Pearson Eta Squared.

The key influence of an explanatory variable is its direct effect on the outcome variables (Field, 2011). Additionally, the effects of covariate and covariate interaction with KC can be included in GLM univariate analysis. This covariance analysis is an extension of the variance analysis to include a covariate/confounder component (Field, 2011). This covariance is linearly related to the dependent variable, and its inclusion in the analysis will minimize the error associated with the covariance analysis (Field, 2011). The test is appropriate since

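### Weight gain, a primary outcome, has no single definition, and its grams-to-discharge form hides a growth effect wherever the discharge weight decides when an infant goes home

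*Combined protocol and SAP*

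**What the plan says.** Section 3.9 b) states: "The primary outcome variables were weight gain and LOS". Weight gain is then described in more than one form:

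- **From baseline to later weighings.** Section 3.16.4 has "outcome weight gain calculated from the weight on discharge", T1 and T2. It names two baselines, birth weight and weight at recruitment. On the unit it says: "Body weight was measured using a T- scale machine and recorded in grams (g".
- **In the analysis table.** Table 3.4 row 2 (section 3.19.1) lists "Weight gain patterns (grams) mean score" for a comparison at T0, T1 and T2.
- **Per day.** Section 1.7.10 defines gain as change in a day. Section 3.16.4 a) has "Weight gain of the infant in daily weight (in a day; 1 day = 24 hours". The booklet item in section 3.9 b) is "weight gain velocity (g/days", and section 3.16.4 also records velocity.

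The discharge rule in section 3.16.4 requires that the infant sucked well, had recently gained more than 15 to 20 g/day on three days running, and "had achieved a predetermined weight of 1.7kg, in accordance with hospital protocol". Section 2.3.7 gives the weight as 1.7 to 1.8 kg. Section 3.4 and the early-discharge slide in Appendix P give 1.8 kg.

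Infants enter at 28 to 36+6 weeks corrected age (section 3.7.1). Follow-up weights are due at 1 and 3 months corrected age, that is 44 and 52 weeks (sections 3.13 and 3.14.5, Table 3.2(b)). Section 3.16.4 says infants were matched by corrected age. Section 3.19.1 plans covariance analysis for confounders in general terms and names no covariates for weight.

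**The concern.** Two things are at stake. First, with grams and grams per day both available, and two baselines, the primary weight result can be chosen after the data are seen. Second, the forms do not answer the same question. A weight that helps to decide when the infant is discharged is not a free measure of growth at discharge. If reaching it is what releases the infant, faster growth shows as an earlier date rather than more grams, and a programme that works could show little or no difference on that form.

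Raw grams gained to T1 or T2 have a separate weakness: they combine growth rate with time since entry, and entry age varies by almost nine weeks.

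**Working it through.** **1. The plan's own figures.** Section 2.4.3 reports that "the KC technique produced a daily weight gain of on average (23.99 vs. 15.58g". The difference is 23.99 − 15.58 = 8.41 g/day, the figure section 3.7.2 cites for sample size, so the cited planning effect is per day. The formula there enters 0.54 with SD 0.8 instead: 2 × 2.802² × 0.64 / 0.54² = 34.46 (34.65 with the rounded 0.29). Both round up to 35 per group, and 35 / 0.70 = 50. The calculation reproduces, but the 0.54 has no stated unit, so it does not settle which form is primary.

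**2. Threshold example.** Days to discharge = (threshold − start) / daily gain. The threshold is 1700 g (section 3.16.4). The 1300 g start is my assumption, and weight alone is taken to decide discharge.

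| | 23.99 g/day | 15.58 g/day |
|---|---|---|
| Days to gain 400 g | 400 / 23.99 = 16.7 | 400 / 15.58 = 25.7 |
| Grams gained at discharge | 400 | 400 |

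The difference in grams is 0. Over a common 25.7 days it would be 8.41 × 25.7 = 216 g. The effect appears as a stay 9.0 days shorter.

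**3. How far this generalises.** A simulation used the same two rates, twice-weekly weighing (section 3.16.4), thresholds of 1.7 and 1.8 kg, and 48 infants per arm. Entry weights, SDs of daily gain (4.5 and 8 g/day) and feeding-readiness times are assumed, because the documents give none for this cohort. *Share kept* is the difference in grams at discharge divided by the difference over a fixed interval equal to the mean control stay.

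| Assumed entry weight | What decides discharge | Share kept |
|---|---|---|
| 1000–1600 g | weight | 4–6% |
| 1000–2400 g | weight, at least 3 days' stay | 14–21% |
| 1000–2400 g (readiness 10 days) or 1000–1600 g (14 days) | weight and feeding readiness | 10–42% |
| 1000–1600 g | weight and feeding readiness, mean 25 days | 30–53% |
| 1700–2400 g | mainly feeding readiness, mean 10 days | about 100% |

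In the first row the difference at discharge is about 14–16 g, against 257–394 g over the fixed interval, and power is about 6%. In the second row power is 8–10%. On the per-day scale the standardised difference would be 8.41 / 8 = 1.05 to 8.41 / 4.5 = 1.87.

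**4. Intervals to T1 and T2.**

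| | Entry 28+0 | Entry 36+6 | Ratio |
|---|---|---|---|
| To 44+0 | 112 days | 50 days | 2.24 |
| To 52+0 | 168 days | 106 days | 1.58 |

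The spread is 112 − 50 = 62 days. At an assumed 20 g/day that is 62 × 20 = 1240 g between infants, against 8.41 × 50 = 420 g for the cited effect over the shortest interval to T1.

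Section 3.18 times the mothers' questionnaires from discharge. If the weights followed that timing, with the 11 to 36 day stays cited in section 1.2, the intervals would be about 11 + 30 = 41 to 36 + 30 = 66 days and 11 + 90 = 101 to 36 + 90 = 126 days (ratios 1.6 and 1.25).

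**The case against.** The strongest reply is that discharge is not the planned comparison. Sections 1.4 and 1.5.2 and Table 3.4 compare groups at T0, T1 and T2, and weights at a fixed corrected age are not cut by the discharge rule. The plan also defines gain per day, which the threshold does not cancel: in the example it still reads 23.99 against 15.58. The effect that leaves the weight outcome is picked up by length of stay, the other primary outcome. Matching and covariance analysis are planned.

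Most of this stands, and it rules out three stronger readings that a reader might infer:

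- **Weight gain is taken only in grams at discharge.** It is not. Discharge is one of three outcome weighings, in one section, beside a per-day definition in several.
- **The discharge rule removes most of the effect for every infant.** The weight is a floor joined with sucking and recent-gain conditions. Section 2.3.5 puts birth weight at about 1500–2500 g for 33 to 36 weeks, so many infants could enter near or above it. The same section gives 1000–1500 g for 28 to 32 weeks, so infants for whom it decides discharge are also plausible.
- **The 2.2-fold and 1.6-fold intervals bias the comparison.** They are extremes across entry ages, not differences between arms. With matched ages they mainly add variance.

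The reply does not choose among the forms or between the baselines. Matching on age does not equalise weight, and no matching procedure is given. The confounder list in section 3.16.4 a) includes gestation and age, but also weight gain itself, and omits recruitment weight.

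**Conclusion.** The primary weight outcome is not uniquely defined: grams or grams per day, with birth or recruitment weight as baseline. Of these forms, grams gained to discharge should not serve as an effect measure. Where the weight threshold decides discharge, it keeps about 4–21% of a growth effect under the assumed entry weights, and the rest moves into length of stay. Where feeding readiness also matters, 10–53% is kept. For infants entering near or above the threshold there is little or no loss. Where this cohort falls depends on its mix of entry weights, which the documents do not state.

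Raw grams to T1 and T2 are a lesser problem, mainly of precision, provided the corrected-age matching worked and the weights were taken at 44 and 52 weeks.

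**What to change.** Amend section 3.16.4 and Table 3.4 row 2 together:

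1. Use recruitment weight as the single baseline.
2. Define the in-hospital outcome as (last in-hospital weight − recruitment weight) / actual days between them, in g/day. Dividing also by mean weight, to give g/kg/day, is a matter of preference.
3. Do not use grams gained to discharge as an effectiveness comparison. Report discharge weight descriptively, alongside length of stay.
4. Compare weight at 44 and at 52 weeks between groups by ANCOVA, adjusted for recruitment weight and corrected age at recruitment.
5. State which of these is the primary weight analysis.
6. Reconcile the discharge weights: 1.7 kg in section 3.16.4, 1.7 to 1.8 kg in section 2.3.7, and 1.8 kg in section 3.4 and Appendix P. Nothing above depends on which applies.

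The cost is wording and reanalysis, since weights, dates and corrected ages are already collected. There are two downsides. Velocity is imprecise for short stays, and it is still partly conditioned on discharge because recent gain is one of the discharge criteria.

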#### a) Infant Outcome Variables Data

In Phase I and Phase III, the outcome data were collected from the control group and experimental group of infants. The outcome data were recorded continuously from the day of recruitment at the corrected age of between 28 to 36/6 weeks of gestation in the NICU until the infants reached 3 months old after discharge. At any stage, if a premature infant in the experimental group did not meet the requirements for research (e.g. deteriorated during KC

or needed phototherapy treatment for jaundice), the infant was excluded from the study. During the two phases, similar outcome variables and confounding variables were obtained. The outcome variables reflected the outcomes of the premature infants. Specifically:

i) KC implementation duration in hours (in hours; 24 hours = 1 day); The duration of KC in the intensive care unit measures the number of hours the infant was attached to or bonded with their mother. According to the posttest it was measured in hours and days per week. According to the World Health Organization (2003), each KC session should ideally last at least 1 hour, in order to get the physiological effects and for brain development and maturation. In this study, the researcher decided to practice accumulative 1 hour per day and accumulative 4 to 5 hours per week (KC duration).

ii) Weight gain of the infant in daily weight (in a day; 1 day = 24 hours)

The weight gain of the premature infant represents the amount the infant's weight increased or decreased in a day. 1 day equal to 24 hours.

iii) The decrease in hospitalization stay or Length of hospitalization stay (LOS) in the NICU (in a day; 1 day = 24 hours);

The length of stay at the NICU measures the number of days the preterm infant was admitted to the intensive care unit and was treated in a day, 1 day equivalent to 24 hours. iv) Confounding variables

All standard demographic and clinical measures assessed by preterm infants with critical care were collected, including:

- demographic data: gestation, age, gender, ethnicity and weight gain for infants;
- type of milk (breastfeeding or formula milk)
- duration of feeding status i.e. week started and week discontinued breastfeeding and mode of feeding, bottle, or spoon-feeding.

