### 3.7.2 Sample Size Calculation for Mother-Infant Dyads

The sample size for mother-infant dyads was calculated using the two-sample independent t-test. This was based on a previous study and this study's primary outcome (Rao, Udani, & Nanavati, 2006). The two-tailed comparison group was used in the sample size calculation using the formula below. The mean difference in weight gain was 8.41 (Rao et. al., 2006) pre and post-intervention, while 0.8 was the standard deviation. These values were applied in the formula based on the study done by Rao et., al (2006).

$$\text{The formula, } n = \frac{2[Z\alpha/2 + Z\beta]^2 S^2}{(\mu_1 - \mu_2)^2}$$

$$\text{Thus, } Z\alpha/2 = 1.96 \quad Z\beta = 0.842$$

$$\mu_1 - \mu_2 = 0.54 \quad S = 0.8$$

$$\text{The formula, } n = \frac{2[1.96 + 0.84]^2 [0.8]^2}{(0.54)^2}$$

$$n = \frac{2 [ 2.802 ]^2 (0.64)}{0.29}$$

$$n = \frac{2 [ 7.85 ] (0.64)}{0.29}$$

$$n = \frac{10.05}{0.29}$$

Thus,  $n = 34.65 = 35$  subjects for each group.

Additional 30% = 50 subjects for each group.

An additional 30% was added to the estimated sample size to account for possible missing values and non- responses. The final sample size calculated was 50 for the sample population, and 50 for the experimental group.

The two groups of preterm infant-mothers were recruited from those who were admitted to the NICU. The first set of samples ( n=50) was recruited from early February 2018 until July 2018. The preterm infant-mother dyads who were admitted within these months were allocated to the control group, while recruitment for the experimental group of preterm infant-mother dyads (n=48) was initiated from early September 2018 until April 2019, after completion of the intervention program for the nurses. In both groups, the sample size for the control group was (n=48) and the experimental group (n=48), for a total sample size of (n=96).

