The control group mothers came for visits and saw their preterm infants once a day for 30 minutes to 1 hour, and exercised KC if they were interested. This was the NICU's routine practice. The control group of mothers continued routine ward practice and standard hospital care. Mothers who declined to participate during the time of the study were excluded. For participation in the study, a small token gift was given to (n=48) mother-infant dyads at the control group.

Upon their premature infant's discharge from the hospital, the mothers were reminded to answer the same standardized questionnaire (QI) for T0, T1, and T2. The following posttest questionnaires (Questionnaire I: enclosed in the envelope) were given to the mothers at the NICU or the Pediatrics Clinic on the 1st and 3rd month, when they came for their premature infant's follow-up, and were returned the same day. Consequently, some of the data were collected and sent by email if the mothers could not keep to the time (received on the same day).

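### Infants in the experimental group can be excluded after enrolment for deterioration or phototherapy, with no matching rule for controls; this can bias weight gain and length of stay towards kangaroo care, by an unknown amount

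*Combined protocol and SAP*

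**What the plan says.** Section 3.16.4 a) describes outcome data collected in both groups, then sets a removal rule for one of them: "At any stage, if a premature infant in the experimental group did not meet the requirements for research (e.g. deteriorated during KC". The same sentence goes on to a second example and to the consequence: "or needed phototherapy treatment for jaundice), the infant was excluded from the study".

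Three other places bear on it.

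- Section 3.16.4, main text: "If any problems were detected during KC, they were either rectified or the preterm infant was disqualified from the study". No arm is named, but the trigger is a problem during KC. Control mothers visited their infants "and exercised KC if they were interested" (3.16.1), so KC was optional there and was the intervention in the other arm.
- Section 3.7.1 lists prolonged phototherapy among the infant exclusion criteria. It applies to both groups, under selection, with no on-study timing.
- Section 3.9 b) names weight gain and length of stay (LOS) as the primary outcomes.

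On numbers, 3.7.2 reports 50 controls recruited and 48 experimental dyads recruited, then that "the sample size for the control group was (n=48) and the experimental group (n=48"). Section 3.16.2 speaks of consent from 48 experimental mothers, and 3.16.4 assigns 48 infants to that group after written consent. For controls, 3.16.4 says "Firstly, all preterm infants between 28 and 36 + 6 days of gestation (n=48) were recruited by the researchers to participate in the study", and 3.16.1 says "a small token gift was given to (n=48) mother-infant dyads at the control group". Section 3.19.1 names the independent t-test, ANOVA/ANCOVA and general linear models, two-tailed at 0.05, but no analysis population.

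**The concern.** Jaundice and deterioration can arise in either group after enrolment. Under the written rules, an experimental infant with such an event leaves the study, while a control with the same event stays unless the problem occurred during optional KC. If the infants who leave would have gained less weight or stayed longer, the remaining experimental group looks better than the group that was enrolled.

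Both primary outcomes are exposed together, because discharge in 3.16.4 depends on sustained daily gain and on reaching a set weight: a slow gainer also tends to stay longer. Excluding infants who deteriorated during KC also removes information on how KC was tolerated. A larger sample does not cure this, and covariate adjustment does not bring back infants who are no longer in the data.

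**Working it through.** **Planned effect, for scale.** Section 3.7.2 uses a difference of 0.54 and SD 0.8, with z-values 1.96 and 0.842. Then n = 2 × (2.802)² × 0.64 / 0.54² = 34.46; the protocol's own rounding gives 34.65. Either way this is 35 per group, and 35 / (1 − 0.30) = 50. The protocol's figures reproduce. The planned effect is 0.54 / 0.8 = 0.675 SD.

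**Bias formula.** If k of N enrolled experimental infants are dropped and would have been worse than those kept by a gap g (in SD), the experimental mean shifts by (k / N) × g in favour of KC. It is zero when g = 0. The documents give neither k nor g, so both are assumptions below.

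**False-positive rate.** Simulation with no true effect: normal outcome, 48 controls, and the k of 48 experimental infants lowest on a latent score removed. The score correlates r with outcome. Two-sample t-test at two-sided 0.05, 60,000 replicates per cell.

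| k of 48 | r = 0.3: gap / shift (SD) / error | r = 0.5: gap / shift (SD) / error |
|---|---|---|
| 2 | 0.64 / 0.026 / 5.2% | 1.06 / 0.044 / 5.7% |
| 3 | 0.61 / 0.038 / 5.4% | 1.00 / 0.063 / 6.1% |
| 5 | 0.56 / 0.059 / 5.8% | 0.94 / 0.098 / 7.9% |
| 10 | 0.51 / 0.107 / 7.7% | 0.85 / 0.177 / 13.3% |

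As a check, k = 5 and r = 0.5 gives 5/48 × 0.94 = 0.098, which is 0.098 / 0.675 = 15% of the planned effect. A second run of 40,000 replicates at r = 0.5 gave 5.7, 6.3, 7.8 and 13.5%. In that run the errors favouring KC, nominally 2.5%, were 4.2, 5.0, 7.0 and 13.3%. With r = 0 the two-sided error stays at about 5%.

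**If 48 is the number left after exclusions**, N = 48 + k. With a gap of 1 SD and a normal approximation:

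- k = 2: shift 2/50 = 0.040 SD, error 5.4%.
- k = 5: shift 5/53 = 0.094 SD, or 0.094 × 0.8 = 0.075 in the protocol's weight units (14% of 0.54), error 7.5%.
- k = 10: shift 10/58 = 0.172 SD, error about 13.5%. Starting from 48 instead, a fixed gap of 1 SD gives 15.7%.

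For LOS, the SDs of 4.3 and 8.64 days quoted in section 1.2 from a cited study serve only as illustration. With k = 5 and a gap of 1 SD, the experimental mean is too short by 0.094 × 4.3 = 0.4 to 0.094 × 8.64 = 0.8 days.

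**Counts side by side.**

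- Experimental: 48 recruited (3.7.2), 48 consented (3.16.2, 3.16.4), 48 final (3.7.2).
- Control: 50 recruited in 3.7.2 but 48 in 3.16.4; 48 final.

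The experimental figures fit zero exclusions, replacement of excluded infants, or a count of completers used throughout. The text does not say which.

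**The case against.** The strongest reply is that the protocol's own counts show no net loss in the experimental group, and that the only visible loss, 50 to 48, is among controls. This stands as evidence that the rule may never have been used. It does not settle the matter: neither a replacement rule nor an exclusion count is given, and the two missing controls are unexplained.

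A second reply is that the phrase about research requirements may mean continued application of common criteria, with examples suited to the KC arm, and that the main text of 3.16.4 names no arm. That reading is possible, and the authors should say whether it is what they did. As written, though, the removal sentence names one group, the other rule needs a KC session to trigger it, and 3.7.1 concerns selection.

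Third, infants had to be clinically stable and tolerating feeds at entry, so many exclusions are unlikely, and planned adjustment for confounders such as gestation could narrow the gap. Both points lower the likely size. Neither replaces a count.

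A reader might infer that infants were in fact removed and that the primary results are inflated. The documents do not show that any infant was excluded. A reader might also take the extreme in which exactly the worst outcomes are dropped, where the error reaches 8.1% for 2 infants and 43.2% for 10. That is a limiting case; nothing in the text indicates that exclusion tracks outcome so closely.

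**Conclusion.** The rule is one-sided as written and the plan keeps no excluded infant in any analysis, so following it can bias both primary outcomes towards KC. The direction rests on the assumption that excluded infants would have done worse. That is plausible for deterioration and only assumed for phototherapy, on which the documents give no outcome figures. The size is unknown: close to nominal error for 2 to 3 exclusions with a moderate association, material only for more exclusions or a stronger link, and nil if exclusion is unrelated to outcome or never occurred. Confidence is high on the wording and low on the size. This should be fixed, because a reader cannot tell which case applies. It is not a demonstrated error that invalidates the results. Daily observation is helpful here: after allocation, infants were such that "they were observed daily, and all observations related to the outcomes of the study were documented in the KCPR booklet", so much of the missing information may be recoverable.

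**What to change.** Section 3.16 describes data collection as finished, so the remedy is disclosure, recovery and analysis.

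1. State the number excluded after enrolment in each arm with reasons. Explain the experimental 48 throughout and the control 50 against 48. Say whether the rules in 3.16.4 and 3.16.4 a) were applied to controls. If no infant was excluded, saying so removes the bias concern.
2. Analyse every enrolled dyad in its group unless consent was withdrawn, with eligibility criteria applied only at entry and identically in Phase I and Phase III. Recover weight to discharge and discharge date of any excluded infant from hospital records. Report 1-month and 3-month data that cannot be recovered as missing, by arm.
3. Report deterioration during KC and discontinuation of KC by arm.
4. Reconcile the phototherapy wording: prolonged treatment in 3.7.1, any treatment for jaundice in 3.16.4 a), and Appendix P, where infants with phototherapy appear under the indications for KC. No clinical rule is proposed, and decisions about KC or phototherapy are unaffected.

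The cost is revised wording and a records search. Values after discharge depend on mothers' booklets and WhatsApp contact, so some may be lost for good. The estimated effect of KC may become smaller.
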